## 2.5 STATISTICAL ANALYSIS

### 2.5.1 Sample Size Determination

In healthy volunteers, the mean (SD) of 30 and 60-days RBC biotin recovery rate is 75% (12.5%) and 50% (10%) (calculated from 24-hour 100% recovery value), respectively. For our first study, evaluating patients with the sickle cell trait SNP, we expect SCD trait to reduce 30 and 60-day recovery to 62% and 25%. A sample size of 15 subjects with sickle cell trait (HbAS) and 20 control African American subjects (HbAA; 10 males and 10 females) would provide 84% power to detect a difference of 13% (SD =12.5%) for 30 days and a power of >95% to detect a difference of 25% (SD = 12.5%) for 60 days RBC recovery rate between AS and AA. This sample size has at least 80% power to detect the interaction between time and genetic group as measure of different recovery rate. We will also recruit an additional 20 Caucasian control (HbAA, 10 males and 10 females) to gain power for testing the effect of other RBC mutations identified in our genome-wide association studies of blood donors (NHLBI RBC-Omics). We will use explanatory analysis for the evaluation of post transfusion recovery of RBCs from subjects with rare variants (<10% of the population) due to a projected small number of subjects carrying such mutations. All 40 control subjects will be tested and selected to not have any of the SNPs that we are studying (listed below).

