This power calculations informs our other planned studies that will compare up to 7 additional single nucleotide polymorphisms (SNPs) patient groups of 15 each, compared with our control groups without the SNPs (n=20 race and gender matched). Successful enrollment of the sickle trait and 7 SNP groups would be 120 total subjects. The eight genetic mutations that we will evaluate may include sickle cell trait (AS), and single nucleotide polymorphisms (SNPs) in ankyrin 1 (ANK1), glucose-6-phosphate dehydrogenase X-linked (G6PD), piezo-type mechanosensitive ion channel component 1 (PIEZ01), spectrin alpha (SPTA), extended synaptotagmin-like protein 2 (ESYT2), Myo9b and SEC14. We may identify additional SNPs as our analysis of the REDS-III GWAS study advances that could replace one of these SNP groups and/or we identify additional non-synonymous SNPs that are associated with susceptibility to hemolysis of stored red blood cells. In addition, we will evaluate 15 subjects on testosterone replacement therapy with 20 controls that are gender and race matched that are not on testosterone replacement therapy.

Each study will be conducted as an independent analysis of 15 subjects with the SNP and 20 race and gender matched subjects without the SNP using power calculations estimated from the SCD trait example above.

**Biotin infusion study:** The study team will target 70 evaluable subjects. The study team will approach 86 subjects with 90% expected to agree to yield 78 subjects who will sign the biotin infusion consent. The study team expects 90% of these subjects to complete the biotin infusion study yielding the target 70 evaluable subjects. The biotin infusion subjects include 20 Whites, 20 African American without sickle cell trait, 15 African Americans with sickle cell trait, and 15 males on testosterone. In addition, 20 subjects with SNPs from the REDS-III RBC-OMICS study will be included for a total of 98 subjects to sign the biotin infusion consent and yield approximately 90 subjects who complete the study.

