### **3. HUMAN SUBJECTS**

The anticipated age range for the study population will be age 18 years or older based upon the target population. Healthy subjects of any ethnic background and with no significant past medical history will be eligible for enrollment.

The proposed study population will consist of potentially 223 (145 from the RBC-OMICs + 78 from Biotin infusion) healthy subjects. In order to achieve this number, it is anticipated that approximately 231 (145 from RBC-OMICs + 86 from Biotin infusion) participants may need to be enrolled into this study to account for subjects who may not qualify the eligibility criteria or not be able to donate blood or are withdrawn for any reasons.

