#### **3.1 SUBJECT POPULATION**

##### **3.1.1 Inclusion of Women and Minorities**

Women and individuals from minority groups especially African Americans or individuals originally from malaria endemic regions who meet the inclusion criteria, and have none of the exclusion criteria, will be enrolled without restriction as dictated by the study protocols. Every effort will be made to enroll participants in this research in a distribution, which mirrors the study population of the Pittsburgh area.

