### Additional Inclusion Criteria for Other Sub-Groups:

#### Healthy volunteers ( subjects who complete the study=20)

- 10 males and 10 females
- Caucasian

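### The 20 race-matched male controls promised to the testosterone group exist only if that group is about half White and half African American, which nothing in the plan requires or adjusts for

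*Combined protocol and SAP*

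**What the plan says.** Section 2.5.1 promises the comparison in these terms: "we will evaluate 15 subjects on testosterone replacement therapy with 20 controls that are gender and race matched". Section 3.2 restricts the testosterone group to men and gives it no race criterion.

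The same section 2.5.1 lists the 70 evaluable infusion subjects as "20 Whites, 20 African American without sickle cell trait, 15 African Americans with sickle cell trait, and 15 males on testosterone". The African American controls are 10 men and 10 women. The White controls are an "additional 20 Caucasian control (HbAA, 10 males and 10 females", and section 3.2 repeats that quota as "10 males and 10 females".

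On race mix, section 3 says "Healthy subjects of any ethnic background and with no significant past medical history will be eligible for enrollment", and section 3.1.1 aims to enrol "in a distribution, which mirrors the study population of the Pittsburgh area" without giving that distribution.

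Section 2.5.2 describes one mixed model, with time, genetic group and their interaction. Subject characteristics appear only in the imputation models of section 2.5.3. Section 1.2 hypothesises that sex and race/ethnicity, as well as genotype, modulate recovery.

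**The concern.** Two promises are made together: 20 controls, and controls matched on sex and race. Sex matching leaves only men, and the roster has exactly 20 male controls. Using every one of them fixes the comparator at half White and half African American. Race matching then depends on the mix of the testosterone group, which the plan leaves open. A man of any other race has no race-matched infusion control at all.

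If the mix is uneven and the analysis follows the section 2.5.2 model as written, part of any race difference in recovery is attributed to testosterone. This affects both the group difference at each time and the group-by-time interaction. The study itself expects race to matter, so the missing term is one its own hypothesis points to.

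**Working it through.** **Counting the controls.** The roster is 20 + 20 + 15 + 15 = 70, so it holds no separate testosterone controls. Male controls number 10 White + 10 African American = 20. The further 20 infusion subjects drawn from RBC-OMICs carry study SNPs, so they are not controls. The RBC-OMICs controls' own visit is a blood draw for laboratory testing only (section 2.2.2) and yields no recovery data.

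**Reproducing the plan's figure.** Inputs from section 2.5.1: 15 v 20, difference 13 points, SD 12.5. Two-sided 0.05 is assumed because sidedness is not stated.
- SE = 12.5 × √(1/15 + 1/20) = 4.27, and noncentrality = 13/4.27 = 3.04 on 33 df.
- Power is 84.0%, which matches the stated 84%.
- At 60 days (25 points, SD 12.5) power is above 99.9%, consistent with the stated figure of more than 95%.

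**Bias without a race term.** With controls at half and half, the share of any White–African American gap left in the estimate is |White share of the testosterone group − 0.5|. For 15:0, 12:3, 10:5 and 8:7 this is |1 − 0.5|, |0.8 − 0.5|, |0.667 − 0.5| and |0.533 − 0.5|. The shares are the same if the majority is African American. The formula covers two races only.

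**Cost of adjusting.** With group and race in the model, information on the group effect adds over races: w = Σ nT·nC/(nT + nC), with nC = 10 in each race, and SE = 12.5/√w on 32 df. The unadjusted value is 15 × 20/35 = 8.571.

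| Split | w | SE | SE increase | Gap left if unadjusted | 30-day power (13 points) | 60-day power (25 points) |
|---|---|---|---|---|---|---|
| 15:0 | 6.000 | 5.10 | 20% | 50% | 69.5% | 99.7% |
| 12:3 | 5.455 + 2.308 = 7.762 | 4.49 | 5% | 30% | 80.2% | over 99.9% |
| 10:5 | 5.000 + 3.333 = 8.333 | 4.33 | 1.4% | 17% | 82.9% | over 99.9% |
| 8:7 | 4.444 + 4.118 = 8.562 | 4.27 | 0.1% | 3% | 83.9% | over 99.9% |

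With complete data and race-by-time terms, the same SE increase applies to every within-subject time contrast.

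**Why a race main effect is not enough.** A race main effect is constant over a subject's visits and cancels from any change over time. A three-time-point check used an assumed race gap of 0, 5 and 10 points and within-subject correlation 0.5. The bias in the group-by-60-day term at 15:0, 12:3 and 10:5 was 5.0, 3.0 and 1.67 points with no covariate. It was the same with a race main effect alone, and zero with race-by-time.

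**The case against.** The strongest reply is that the plan already controls for race by saying the controls are race matched, and that the 10 + 10 pool can deliver this if the testosterone men are recruited at about 8:7. Nothing forbids that. This stands as far as it goes: the documents show that matching is not secured, not that it will fail. The bias figures apply only if the mix turns out uneven and the analysis is unadjusted.

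The comparator is also inferred. No section names these 20 men as the testosterone controls, and section 5.1 speaks loosely of recalled donors possibly serving as the biotin control. That wording is ambiguous, but the roster has no control places beyond the 20 White and 20 African American subjects, so such donors could only fill those places.

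A reader might infer that the testosterone model wrongly omits race. The documents do not go so far: section 2.5.2 is written for genetic group, and no testosterone model is set out. The accurate statement is that the only stated model lacks the term.

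A reader might also infer that a stated testosterone power is wrong. None is stated. The carry-over sentence, "using power calculations estimated from the SCD trait example above", concerns subjects with a SNP.

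Nor do the documents support saying that interaction power drops below 80%. The plan says "This sample size has at least 80% power to detect the interaction between time and genetic group", which is a floor and cannot be scaled down as if exact. Suppose the sickle-trait values apply, with no early gap, 25 points at 60 days, SD 12.5 at both times and zero within-subject correlation (assumed). The early-to-60-day contrast at 15:0 then has noncentrality 25/(5.10 × √2) = 3.46 and about 92% power after adjustment.

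**Conclusion.** The concern holds as a gap in specification. The promise of 20 sex- and race-matched controls can be kept with the planned roster only at a race mix near half and half, and the plan neither sets that mix nor adjusts for departures from it. Unadjusted, between 3% (8:7) and 50% (15:0) of any race gap in recovery would enter the testosterone estimate. The size and direction of the gap, the race mix and the expected testosterone effect are all absent from the documents, so no bias in points can be stated.

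If the sickle-trait planning values are meant to apply, adjusted 30-day power is about 70%, 80%, 83% or 84% across the four splits, rather than a flat 84%. Power at 60 days stays at 99.7% or more. Near an even split both problems are negligible. The priority is minor because testosterone is a secondary objective.

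**What to change.** - Name the 20 male infusion controls, 10 White and 10 African American, as the testosterone comparator.
- Write out the testosterone mixed model, with race and race-by-time alongside time, group and their interaction.
- Where feasible, set a recruitment target of about half White and half African American for the testosterone group, so that the promised matching is delivered by design.
- Say how men of other races are handled, since two-category adjustment does not cover them.
- If the sickle-trait planning values are meant to apply, give 30-day power for the expected mix. Otherwise give the difference detectable with 80% power at SD 12.5: 14.7, 13.0, 12.5 or 12.3 points at 15:0, 12:3, 10:5 or 8:7.

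The analysis change is wording only, because demographics are already collected at Visit 1. With time in three categories the model gains three parameters. The price is precision when the mix is uneven, as tabulated, and an assumption that the testosterone effect is the same in both races. The recruitment target costs almost no power but may slow enrolment.

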REDS-III RBC-OMICs study: The study team will target 105 subjects (with SNPs) who will sign the REDS-III RBC-OMICs consent. Included in the 105 are the 20 subjects who will also sign the biotin infusion consent. In addition, approximately 40 RBC-OMICs control subjects will be tested and selected to not have any of the SNPs that we are studying. An RBC-OMICs control subject will perform the same blood draw study visit procedures at different times on the same day as an RBC-OMICs subject with one of the targeted SNPs. The study team will compare the red blood cells biophysical properties in an RBC-OMICs control subject to an RBC-OMICs subject with one of the targeted SNPs. The RBC-OMICs control subjects may be asked to return up to a maximum of 6 times in one year to perform additional optional RBC-OMICs control blood draw visits at MUH-CTRC. There will be a maximum of 6 number of blood draw visits for each of the 40 RBC-OMICs control subjects.

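### Section 2.5.1 gives every additional SNP study 15 infused carriers and the sickle-trait power, but plans only 20 additional-SNP infusions in total

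*Combined protocol and SAP*

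**What the plan says.** Section 2.5.1 (Sample Size Determination) powers the sickle-trait comparison on recovery of transfused labelled cells. With 15 HbAS subjects and 20 HbAA controls it claims 84% power for a 13-point difference at 30 days (SD 12.5), and more than 95% for "a difference of 25% (SD = 12.5%) for 60 days RBC recovery rate between AS and AA". The same paragraph gives the healthy-volunteer SD at 60 days as 10, not 12.5.

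It then extends this to as many as seven further SNPs: "Each study will be conducted as an independent analysis of 15 subjects with the SNP" and 20 race- and gender-matched controls, "using power calculations estimated from the SCD trait example above". The head count is "Successful enrollment of the sickle trait and 7 SNP groups would be 120 total subjects".

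The infusion plan later in the section is different. It lists 70 evaluable subjects (20 White, 20 African American without sickle trait, 15 with it, 15 men on testosterone) and adds "20 subjects with SNPs from the REDS-III RBC-OMICS study will be included for a total of 98 subjects" signing consent, with about 90 completing. The REDS-III RBC-OMICs paragraph targets 105 SNP carriers and says "Included in the 105 are the 20 subjects who will also sign the biotin infusion consent". Section 2.2.2 describes the RBC-OMICs visit as a small blood draw for in vitro testing, whose results may identify a candidate for reinfusion.

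Section 2.4 defines the primary endpoint as labelled-cell recovery over 60 days after transfusion and treats each group as a separate study.

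**The concern.** The section gives two carrier counts that cannot both apply to the primary endpoint. Fifteen carriers per group over eight groups is 120. The planned infused carriers number 35: 15 with sickle trait and 20 with any other SNP. The other 85 RBC-OMICs carriers (105 − 20) give blood for laboratory tests and cannot contribute to a recovery estimate.

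A reader would credit every SNP comparison with 84% and above 95% power, and a null result could be taken as adequately powered evidence of no effect. No section says how the 20 infusions are divided among SNPs, so the precision of any SNP-specific recovery estimate cannot be judged in advance.

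**Working it through.** **Inputs.** From Section 2.5.1: differences of 13 points (30 days) and 25 points (60 days); SD 12.5, or 10 at 60 days; 15 carriers and 20 controls; 20 additional-SNP infusions; 90% completion stated for the 78 consenting subjects. From Section 2.5.2: significance level 0.05. Two-sided testing is assumed because sidedness is not stated.

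**Method.** Two-sample t-test with equal variances, n₁ carriers and n₂ controls. SE = SD × √(1/n₁ + 1/n₂), degrees of freedom n₁ + n₂ − 2, noncentrality = difference/SE, power from the noncentral t distribution.

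**Reproducing the plan's figures.** For 15 vs 20 at SD 12.5, SE = 12.5 × √(1/15 + 1/20) = 4.27.
- 30 days: 13/4.27 = 3.04, power 84.0%. The stated 84% is right for this size.
- 60 days: 25/4.27 = 5.85, power above 99.9%. The stated figure is met.

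**Counts.**
- Needed: 8 × 15 = 120 carriers, of whom 7 × 15 = 105 have an additional SNP.
- Infused: 15 + 20 = 35, of whom 20 have an additional SNP.
- The 20 agrees with the totals around it: 70 + 20 = 90 and 78 + 20 = 98.
- With one SNP per carrier, 20/15 rounds down to 1 group of 15. The Synopsis admits subjects with one SNP or more, but two groups of 15 from 20 people would need at least 15 + 15 − 20 = 10 carrying both. No section plans this.

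**30 days (13 points, SD 12.5).** The stated 84% needs 15 carriers vs 20 controls (84.0%; 14 gives 82.5%) or 11 vs all 40 controls pooled (85.0%; 10 gives 82.2%). Either way, 20 carriers support one SNP at 84%.

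**60 days (25 points).**

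| Carriers | SD 12.5, 20 controls | SD 12.5, 40 controls | SD 10, 20 controls | SD 10, 40 controls |
|---|---|---|---|---|
| 5 | 96.9% | 98.5% | above 99% | above 99% |
| 4 | 93.7% | 96.1% | above 99% | above 99% |
| 3 | 86.9% | 90.4% | 97.0% | 98.3% |
| 2 | 72.8% | 76.8% | 89.3% | 92.0% |

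SNPs that can keep more than 95%, with all 20 completing or with 18 (an assumption: 20 × 0.9):
- SD 12.5, 20 controls: 5 carriers each, so 20/5 = 4 SNPs, or 3 on 18.
- SD 12.5, 40 controls: 4 carriers each, so 20/4 = 5 SNPs, or 4 on 18.
- SD 10: 3 carriers each, so 6 SNPs on 20 or on 18.
- Seven SNPs: 20/7 = 2.86, so at least one SNP has two carriers or fewer, and the best case for two is 92.0%.

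The 18 may be pessimistic, since the section's total of about 90 completers (70 + 20) fits nearly all 20 completing.

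**Without the 25-point assumption.** The smallest 60-day difference detectable with 80% power, and the 95% confidence interval half-width (critical t × SE):

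| Comparison | Detectable, SD 12.5 | Detectable, SD 10 | Half-width, SD 12.5 |
|---|---|---|---|
| 15 vs 20 | 12.3 | 9.9 | 8.7 |
| 5 vs 20 | 18.3 | 14.6 | 12.9 |
| 4 vs 40 | 18.8 | 15.0 | 13.2 |
| 3 vs 20 | 22.7 | 18.2 | 16.1 |

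**Illustration only.** An even split over seven SNPs, which no section plans, gives two or three carriers each. Against 20 controls at SD 12.5, power is 27% to 36% at 30 days and 73% to 87% at 60 days.

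**The case against.** The best defence is that the 105 is the in vitro target. Seven groups of 15 is exactly the RBC-OMICs carrier number in Sections 2.5.1 and 3.2, so the 15-per-SNP count is filled for laboratory testing, which Aim 1 also covers. No section says that 120 people will be infused, and the 20 fits the surrounding totals and looks deliberate. This probably explains how the text arose, and it suggests that the power wording, not the infusion number, is out of step. It does not remove the fault: the power attached to each group of 15 is in vivo power.

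Several other points temper the finding:
- Section 2.5.1 adds 20 Caucasian controls "to gain power for testing the effect of other RBC mutations identified in our genome-wide association studies of blood donors", and Section 2.4 mentions pooled controls. Two SNPs with 10 carriers each against 40 controls would keep 82% at 30 days, so the 30-day shortfall for a second SNP could be only two points. The 15-per-SNP size would still not be met, and the same section also specifies 20 matched controls per SNP.
- Section 2.2.1 foresees a high- and low-risk SNP profile for reinfusion. All 20 carriers analysed as one group would have 89% (vs 20) or 96% (vs 40) at 30 days. Section 2.4, however, makes each group a separate study.
- Section 2.5.1 sets a separate analysis for rare variants, where few carriers are expected. This may exempt some SNPs from the powered comparison, but it names none and gives no size.
- The pilot label, the exploratory aim and the wording that up to seven SNPs may be studied limit how many go forward. They do not alter the size and power claimed for each one that does.
- The planned analysis is a mixed model over three time points, and 30 days is not singled out for a separate test. The t-tests follow the plan's own single-time-point power figures. The claimed interaction power of at least 80% cannot be recomputed, because no within-subject correlation is given.

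**Conclusion.** The concern holds. With one SNP per carrier, the 20 planned infusions can give at most one additional SNP the stated 15 carriers, and at most one the stated 84% at 30 days, even with all 40 controls. At 60 days, the time point that Sections 2.4 and 2.5.2 single out, the damage is smaller. Three to five SNPs could keep more than 95% at SD 12.5, and six at SD 10, but not seven under any split. These 60-day figures rest on a 25-point difference assumed for sickle trait, with no stated basis for the other SNPs. All figures assume two-sided t-tests with equal variances. The documents do not state outright which count should govern, although the infusion totals consistently use 20.

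**What to change.** Reconcile the 15-per-SNP and 120 counts with the 20 infusions; which one changes is the sponsor's decision. If the 20 are kept:

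1. Limit the 15-versus-20 statement and its 84% and above-95% power to sickle trait versus HbAA, and to any additional SNP that will have 15 infused carriers.
2. State how the 20 infusions are allocated, by SNP or by risk profile.
3. State which controls are used (20 matched or 40 pooled), which 60-day SD applies (10 or 12.5), and the basis for the 60-day difference assumed for SNPs other than sickle trait.
4. Restate the resulting power, 60 days first and then 30 days.
5. Report in vivo results for SNPs below that size as descriptive estimates with 95% confidence intervals.

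The cost is protocol and SAP wording plus one restated calculation, with no extra subjects. The price is a less favourable stated power and fewer SNP-specific in vivo claims. If the 15 per SNP is kept instead, seven groups would need 105 infused completers, or 105/0.9 = 117 consenting at 90% completion.

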
Study Endpoints:
	
The primary endpoint is the labeled red blood cell recovery rate over 60-days post transfusion of 35-42 day stored Bio-RBCs from blood donors with specified genetic mutations, compared with control subjects without the specified mutation.
 
This protocol may evaluate up to eight (8) genetic mutations as independent studies, compared with pooled control groups (without any of the identified SNPs) as well as a group of subjects on testosterone replacement therapy. The eight genetic mutations may include sickle cell trait (AS), and single nucleotide polymorphisms (SNPs) in ankyrin 1 (ANK1), glucose-6-phosphate dehydrogenase X-linked (G6PD), piezo-type mechanosensitive ion channel component 1 (PIEZ01), spectrin alpha (SPTA), extended synaptotagmin-like protein 2 (ESYT2), Myo9b and SEC14. All control subjects will be tested and must not have any of these SNPs. We may identify additional SNPs as our analysis of the REDS-III GWAS study advances that could replace one of these SNP groups and/or we identify additional non-synonymous SNPs that are associated with susceptibility to hemolysis of stored red blood cells. In addition, we will evaluate 15 subjects on testosterone replacement therapy with 20 controls that are gender and race matched that are not on testosterone replacement therapy.
 
The secondary endpoints include effects of gender on post transfusion recovery, the 2-4 hours post transfusion survival of fresh or stored Bio-RBCs, and to determine the association between in vitro correlates of the RBC storage lesion (e.g., storage and stress-induced hemolysis, membrane microvesicle formation) and post transfusion recovery.
 
A subset of recalled donors with these SNPs will be asked to provide a blood sample to be tested for functional effects on red cell biophysical properties, stability in storage, and release of eDAMPs, and compared to donors with no implicated SNPs. We will develop an enriched SNP profile that defines a high risk and low risk donor for further evaluation in autologous reinfusion studies as a low cost precision transfusion medicine array.

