## **1.2 SPECIFIC AIMS**

### Hypothesis:

We hypothesize that genetic mutations and biologic variables (sex, race/ethnicity) in blood donors modulate the recovery of red blood cells after cold storage and transfusion.

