## **2.4 STUDY ENDPOINTS**

### Primary Endpoint:

The primary endpoint is the labeled red blood cell recovery rate over 60-days post transfusion (using data from 2-4 hours, 1 and 2 month) of 35-42 day stored Bio-RBCs from blood donors with specified genetic mutations, compared with control subjects without the specified mutation.

This protocol may evaluate up to eight (8) genetic mutations as independent studies, compared with pooled control groups, as well as a group of subjects on testosterone replacement therapy. The eight genetic mutations that we will evaluate may include sickle cell trait (AS), and single nucleotide polymorphisms (SNPs) in ankyrin 1 (ANK1), glucose-6-phosphate dehydrogenase X-linked (G6PD), piezo-type mechanosensitive ion channel component 1 (PIEZ01), spectrin alpha

(SPTA), extended synaptotagmin-like protein 2 (ESYT2), Myo9b, and SEC14. We may identify additional SNPs as our analysis of the REDS-III GWAS study advances that could replace one of these SNP groups and/or we identify additional non-synonymous SNPs that are associated with susceptibility to hemolysis of stored red blood cells. In addition we will evaluate 15 subjects on testosterone replacement therapy with 20 controls that are gender and race matched that are not on testosterone replacement therapy. Each group will be considered a separate study for statistical purposes. Controls will be selected based on not having any of the SNPs that will be evaluated in these studies.

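### The primary endpoint compares each SNP group with pooled controls, the sample-size section uses 20 matched controls, and the analysis section neither names a control set nor adjusts for race or sex

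*Combined protocol and SAP*

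**What the plan says.** **Endpoint wording.** Section 2.4 (Primary Endpoint) treats up to eight mutations "as independent studies, compared with pooled control groups, as well as a group of subjects on testosterone replacement therapy". The synopsis (Study Endpoints) has each mutation "compared with pooled control groups (without any of the identified SNPs" being studied. Sickle trait is one of the eight in both places. Neither place mentions matching for the SNP comparisons; race and gender matching appears there only for the testosterone group.

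**Sample-size wording.** Section 2.5.1 powers sickle trait with 15 HbAS carriers against 20 African American HbAA controls. It then says every SNP study is an "independent analysis of 15 subjects with the SNP and 20 race and gender matched subjects without the SNP". The same section plans to "recruit an additional 20 Caucasian control (HbAA, 10 males and 10 females) to gain power for testing the effect of other RBC mutations", and adds: "All 40 control subjects will be tested and selected to not have any of the SNPs that we are studying".

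**Analysis wording.** Section 2.5.2 fits a mixed-effects model with time, genetic group and their interaction. It does not say which controls enter and lists no race or sex term.

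**Race.** The hypothesis in section 1.2 is that "genetic mutations and biologic variables (sex, race/ethnicity) in blood donors modulate the recovery of red blood cells" after storage and transfusion. Section 3.2 requires every sickle-trait subject to self-identify as African American and sets one control group as Caucasian. Section 3 admits any ethnic background.

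**The concern.** Sections 2.4 and 2.5.1 give different control sets for the same primary test, and section 2.5.2, where the choice ought to be settled, is silent. An analyst could follow either section and be within the protocol, and could choose after seeing the data.

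The choice matters most for sickle trait. Every carrier is African American. If the comparator is the whole control pool, half of it is Caucasian, and the model has no term to separate race from genotype. By the plan's own hypothesis race may influence recovery, so a race difference could be reported as a sickle-trait effect.

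For the other SNPs the question is how many controls enter and of which race. The stated power describes only one of the possible answers.

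**Working it through.** **Inputs**
- 15 carriers and 20 matched controls per SNP study; 40 infusion controls in all, 20 African American and 20 Caucasian (2.5.1).
- 30-day difference 13 points, SD 12.5, stated power 84%; 60-day difference 25 points, SD 12.5, stated power above 95% (2.5.1).
- Significance at P < 0.05 (2.5.2). Sidedness is not stated; two-sided is assumed because it reproduces the plan's figure.
- 20 infusion subjects with SNPs from the RBC-Omics cohort, in total (2.5.1).
- Assumption: an African American/Caucasian difference D of 5, 10 or 15 points. The documents give no value.

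**Step 1. Reproduce the stated power.** For a two-sample t-test, SE = SD × √(1/n₁ + 1/n₂), and power comes from the noncentral t distribution with n₁ + n₂ − 2 degrees of freedom.
- 15 vs 20: SE = 12.5 × √(1/15 + 1/20) = 4.27; 13/4.27 = 3.04; power 84.0%. The stated 84% reproduces, so it rests on 20 controls.
- 25 points, 15 vs 20: power above 99.9%, consistent with the stated figure.

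**Step 2. Same inputs with 40 controls.**
- 15 vs 40: SE = 12.5 × √(1/15 + 1/40) = 3.78; 13/3.78 = 3.44; power 92.1%.
- 25 points: above 99.9% again.

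**Step 3. Sickle trait against all 40 controls, no race term.** The mean of a half-and-half control group differs from the African American control mean by D/2, so the contrast is biased by D/2. Mixing two races also widens the control SD to √(12.5² + (D/2)²). Simulated t-tests with no true trait effect (15 carriers, 20 + 20 controls, within-race SD 12.5) give:

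| Assumed D (points) | Bias D/2 (points) | Control SD | False-positive rate |
|---|---|---|---|
| 5 | 2.5 | 12.7 | about 9.5% |
| 10 | 5.0 | 13.5 | about 22% |
| 15 | 7.5 | 14.6 | about 40% |

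**Step 4. The other SNPs, 40 controls with race as a fixed term** (13 points, SD 12.5, 15 carriers).
- Carriers split evenly by race: SE 3.78, power about 92%.
- Carriers all of one race: the 20 controls of the other race tell us nothing about the carrier contrast beyond the residual variance. SE stays at 4.27 and power is about 85%.

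**Step 5. Carrier numbers actually planned.** 20 carriers over seven SNPs is 20/7 ≈ 2.9, about 3 per SNP if spread evenly. At 13 points and SD 12.5:
- 3 vs 20: SE = 12.5 × √(1/3 + 1/20) = 7.74; power about 36%.
- 3 vs 40: SE = 12.5 × √(1/3 + 1/40) = 7.48; power about 40%.

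**The case against.** The best defence is that the sickle-trait contrast is already settled. Section 2.5.1 powers it between HbAS and African American HbAA subjects, section 3.2 recruits those controls to match the carriers on sex and age, and section 2.5.1 gives the Caucasian controls a different purpose, the other mutations. No sentence says that the pooled set numbers 40. Pooled could mean a shared pool from which matched sets are drawn. Much of this stands: a reader might infer that the sickle-trait analysis as planned is biased by race, and the documents do not support that. They support a bias only if the endpoint wording governs. But that wording defines the primary comparison, covers sickle trait, and is not overridden in 2.5.2, so the conflict remains.

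Three other inferences go too far.
- **The Caucasian controls add nothing under matching.** Section 3.2 sets no race limit on RBC-Omics carriers, so Caucasian carriers would need Caucasian controls.
- **Using 40 controls lifts power from 84% to 92% for every SNP.** This holds only at the 13-point 30-day effect, with 15 carriers per SNP spread over both races. At the planned 25-point 60-day effect, power exceeds 99.9% under either rule. With about 3 carriers per SNP, neither set gives adequate power at 13 points.
- **The false-positive rate reaches about 25% or 49% for race differences of 10 or 15 points.** Those values come from shifting the control mean while holding the SD at 12.5. They ignore the wider spread of a mixed control group.

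Matching on race and gender is also a legitimate design in its own right. Nothing here shows that 40 adjusted controls must be preferred to 20 matched ones.

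**Conclusion.** The inconsistency is real and should be fixed. Sections 2.4 and 2.5.1 name different control sets for the primary test, and 2.5.2 neither chooses between them nor adjusts for race or sex.

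The main consequence is for sickle trait, and it rests on three conditions: the endpoint wording is followed, pooled means all 40 controls, and recovery differs by race. The bias is then half the race difference. The size of that difference is assumed throughout.

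For the other SNPs the control rule needs stating, but the small number of carriers planned limits those tests more than the choice of controls does. In a single-centre pilot, with the intended sickle-trait comparator recoverable from 2.5.1, this falls short of a defect that invalidates the plan.

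**What to change.** 1. In 2.4, 2.5.1 and 2.5.2, and in the synopsis to match, name one control set for each contrast.
2. For sickle trait, replace the pooled wording with the 20 African American HbAA controls. The stated 84% already assumes them.
3. For the other SNPs, state either the race- and gender-matched set or all 40 SNP-free controls. Wherever controls of both races are used, add race and sex as fixed terms in the mixed model. Say how carriers with no same-race controls will be handled.
4. Restate power for the chosen set and for the carrier numbers actually planned, with the assumed split of carriers by race.

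The cost is protocol wording and two model terms built on demographics already collected at Visit 1. No extra subjects are needed. The downside is small: two more parameters in a small sample, and no guaranteed gain in power.
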